8.2 Sample Size/Accrual Rate

Participants will continue to be enrolled and monitored for toxicity per the above criteria until 30 patients in arm 1 and 15 patients in arm 2 have completed the course of head and neck radiation as evaluable patients. Patients will be randomized by computer in a 2:1 fashion. Per our current database, the clinic is treating approximately 60 eligible patients per year. As such, accrual should take no longer than 12 months but will be allowed to extend to up to 24 months without closing the study.

Initial sample size for this pilot study was estimated as if this study was conducted as a phase II study. Sample size calculation was determined using significance/alpha (α) of 0.05, to at least detect a difference in incidence of 45% and power (β) of 80%. In general, rates of clinically bothersome grade II dermatitis in the literature appear to be approximately 65%. Based on our preclinical study with animal and human skin models, we expect 20% of the Dermaprazole arm to have CTCAE grade II or higher RD. Given these values, we calculated our final sample size to be approximately 39 and we aim to enroll 45 subjects.

8.3 Analysis of Primary and Secondary Endpoints

Descriptive and summary statistics will be computed for demographic and clinical data of all subjects enrolled in the study to describe the study sample.

Toxicity will be reported as the frequency of each adverse event according to the CTCAE version 5.0 as well as the grade of each recorded adverse event (38). Generally, adverse events in this system are graded from 1 to 5, with 1 corresponding to either mild or asymptomatic clinical manifestations of toxicity and 5 corresponding to death related to the

Page 15 of 23

adverse event (see Appendix 2). Clinically relevant toxicity will be defined as grade 2 or higher, while severe toxicity will be defined as grade 3 or higher. Acute toxicity will be defined as adverse events that occur during or within 90 days after completing radiation therapy. We will consider this intervention safe if there is a grade 1 toxicity rate of <50%, a grade 2 or higher toxicity rate of <10% and no grade 3 or higher events.

Percentages of patients enrolled per month will be recorded. If the enrollment time exceeds 24 months, the study will be considered not feasible as written. Percentage of patients not enrolled will be summarized by cause.

Quality of life will be measured with the use of SkinDex16 questionnaires filled out by the patient at baseline, throughout treatment, at the completion of radiation treatment, and at each follow up visit subsequently. We will also consider the compliance to questionnaire completion and within questionnaires completion rates. This will be reported as the average proportion of questions within each form completed properly, without errors. As long as the rates are not below the minimum threshold defined above, the study will be considered feasible.

All analyses outside of the primary endpoint will be considered exploratory in nature. Chi square and t-test will be used to evaluate differences in categorical and numerical values between arms. Subgroup analyses for BMI, total dose, and comorbidity will be conducted. We will also evaluate the incidence of RD for specific radiation skin dose stratification by reviewing the V20 to V80 in 5 Gy increments reaching a skin shell representing the thickness between the skin and the "skin minus 3 millimeters" and the "skin minus 5 millimeters." This will be done on both the original dosimetry as well as a recalculated plan from the resimulation scan.

We will also evaluate any statistically significant differences in both the absolute numbers and relative changes of the lab values: CRP, TNFa, IL-1b, IL-6 at each of the 3 time points in which they are drawn for each arm.

All statistical tests will be two-sided. We will report comparative data in good faith and emphasize that the primary intention of this study is to understand the safety and tolerability profile of Dermaprazole.

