This conviction stems from our extensive preclinical study that demonstrated pleiotropic beneficial effects of PPIs in regulating tissue inflammation and fibrosis induced by chemotherapy or ionizing radiation. Our most recent data in a mouse model of RD shows that PPIs have remarkable effect in protecting the skin from the harmful effects of ionizing radiation. Primarily, we aim to evaluate the safety and tolerability of Dermaprazole cream in HNC patients at risk of developing RD. This study will consist of 2 arms: arm 1 consists of 30 HNC patients who will be using Dermaprazole twice daily while arm 2 consists of 15 HNC patients using Aquaphor, the current clinical standard of care.

We will assess for treatment-related adverse effects including burning, itching, tenderness, rash, and any other local or systemic allergic reactions. In addition, we will collect patient- reported quality of life questionnaire (skindex16) throughout the treatment period and during the follow up period. Furthermore, inflammatory markers including CRP, TNFa, IL-1b, and IL-6 will be drawn, pre-treatment, in the last week of treatment, and post-treatment. If found safe and effective, our product has the potential to dramatically impact clinical practice by significantly decreasing treatment-related morbidity and allowing adherence to the prescribed dose of RT which may otherwise be interrupted because of severe dermatitis.

We will track the dose delivered to the skin in the treatment planning system and repeat a simulation in the last week of therapy to assess the accuracy of this tracking and possible RD correlation with updated dosimetry from the new scan.

STUDY SCHEMA

Page 3 of 23

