3.1 Study Disease

Radiation dermatitis is an expected complication of radiotherapy that can lead to worse patient-reported quality of life during treatment and worse cosmesis, particularly in obese patients. Patients within the Bexar County Health System are more likely to have risk factors associated with radiation dermatitis, including obesity and diabetes. While our mostly low socioeconomic status patients stand to benefit the most from upfront therapy in order to prevent later cancer-related morbidity and mortality, they are also more likely to suffer from acute treatment-related morbidity, including radiation dermatitis.

Given the unmet medical need for therapies to address radiation dermatitis, our basic science team has been investigating candidate drugs to mitigate the problem. After screening a library of 130,000 compounds, we found that proton pump inhibitor (PPIs) have previously unrecognized yet potent effect in modulating inflammation and fibrosis induced by chemotherapy and ionizing radiation. Radiation-induced dermatitis occurs in most patients following radiotherapy. According to the NCI-CTCAE (Services, 2017) and RTOG (J. D. Cox, 1995) scoring systems, mild dermatitis (Grade I) is characterized by mild redness (erythema), epidermal thickening (hyperkeratosis) or dry desquamation and appears shortly after initiation of T. Moderate dermatitis (Grade II) occurs within two weeks of radiotherapy and manifests painful and intense erythema, loss of hair from the root (epilation), blisters and edema. Of note, the presence of grade II toxicity is generally regarded as clinically significant toxicity. In severe dermatitis (Grade III and IV), moist desquamation occurs excessively and may lead to persistent inflammation, full-thickness skin necrosis and severely painful ulceration that is prone to infection. The acute effects occur almost immediately at radiation doses between 2 and 40 Gray (2-40 Gy) whereas chronic effects occur several months-to-years after exposure to high radiation doses (> 45 Gy) and typical skin changes include atrophy, scarring and spider veins (telangiectasia) (S. R. Hymes, 2006).

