5.5 Assessments & Labs During Treatment

Weekly on-treatment assessments are as follows:

- Focused skin exam
- Adverse event/toxicity evaluation, including CTCAE version 5 evaluation of radiation dermatitis with note of components (erythema, epilation, fibrosis, etc)
- SkinDex16 questionnaire
- Photographic documentation of skin reaction with dermatologist's evaluation of CTCAE version 5 from this photography (photography may be discontinued if dermatitis radiation has resolved, or does not occur, at the discretion of the treating investigator or Principal Investigator)
- Compliance diary
- WBC, Hgb, ALT, AST, creatinine and calcium taken from standard care clinical labs
- Research Blood Draw to Central Lab: CRP, TNFa, IL-1b, IL-6 (in the last week of radiation and at 2 weeks after end of radiation)

Page 10 of 23

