An adverse event (AE) is defined as any untoward or unfavorable medical occurrence in a human subject, including any abnormal sign (for example, abnormal physical exam or laboratory finding), symptom, or disease, temporally associated with the subject's participation in the research, whether or not considered related to the subject's participation in the research.

The adverse event (AE) collection/reporting period will begin with the first day of treatment with radiation or chemotherapy. AEs after study registration but prior to the first day of study treatment will be captured as ongoing concurrent secondary diagnoses and symptoms present at the start of study.

Serious Adverse Event Definition: is any adverse event that:

- 1. results in death;
- 2. is life-threatening (places the subject at immediate risk of death from the event as it occurred);
- 3. results in inpatient hospitalization or prolongation of existing hospitalization;
- 4. results in a persistent or significant disability/incapacity;
- 5. results in a congenital anomaly/birth defect; or
- 6. based upon appropriate medical judgment, may jeopardize the subject's health and may require medical or surgical intervention to prevent one of the other outcomes listed in this definition.

Page 18 of 23

Unanticipated Problems Involving Risks to Subjects or Others Definition:

Unanticipated problem involving risk to subjects or others includes any incident, experience or outcome that meets all of the following criteria:

A. unexpected (in terms of nature, severity, or frequency) given

- (a) the research procedures that are described in the protocol-related documents, such as the IRB-approved research protocol and informed consent document; and
- (b) the characteristics of the subject population being studied (note: the unfounded classification of a serious adverse event as "anticipated" constitutes serious non-compliance);

B. definitely related or probably related to participation in the research; and C. suggests that the research places subjects or others at a greater risk of harm (including physical, psychological, economic, or social harm) than was previously known or recognized.

Expected adverse events are those that have been previously identified as resulting from administration of topical or radiation therapy.

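### The section 8.3 safety criterion does not say whether events must be attributed to the cream; read literally, it conflicts with the dermatitis rate that section 8.2 plans for

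*Combined protocol and SAP*

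**What the plan says.** Section 8.3 sets three conditions for calling the intervention safe: grade 1 toxicity below 50%, "a grade 2 or higher toxicity rate of <10% and no grade 3 or higher events". No condition mentions relatedness, and no denominator is given.

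The wording around the rule is broad:
- The same paragraph of 8.3 says "Toxicity will be reported as the frequency of each adverse event according to the CTCAE version 5.0" and "Acute toxicity will be defined as adverse events that occur during or within 90 days after completing radiation therapy".
- Section 10.3 defines an adverse event as one that counts "whether or not considered related to the subject's participation in the research".
- Section 5.5 lists, among the weekly assessments, "Adverse event/toxicity evaluation, including CTCAE version 5 evaluation of radiation dermatitis".
- Section 3.1, describing dermatitis grades, says that "the presence of grade II toxicity is generally regarded as clinically significant toxicity".

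Section 8.2 states the planning assumption: "we expect 20% of the Dermaprazole arm to have CTCAE grade II or higher RD".

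Other places are narrower. The study summary says "We will assess for treatment-related adverse effects including burning, itching, tenderness, rash, and any other local or systemic allergic reactions". Section 5.6 describes follow-up as assessing intervention-related tolerance. Section 8.1 limits its 50% rule to intervention-related toxicity and its early-stopping rule to treatment-related serious events. Section 10.3 has a five-level attribution scale, from definite to unrelated. Nothing in 8.3 refers to that scale or to 8.1.

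**The concern.** Section 8.3 closes by calling safety and tolerability the main purpose of the study, and this rule is its stated safety verdict. Radiation dermatitis of grade 2 or higher is also the efficacy outcome, and the plan expects it in one Dermaprazole patient in five. If those cases count as toxicity, the planned efficacy result is twice the safety limit. If only events caused by the cream count, the dermatitis that radiation would have produced anyway drops out.

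The rule does not choose between these readings. The choice could therefore be made after the data are seen, and it can reverse the conclusion.

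**Working it through.** **Inputs.** 30 evaluable Dermaprazole patients and 15 Aquaphor patients (8.2); grade 2 or higher dermatitis of 20% and 65% (8.2); limit strictly below 10% (8.3). Assumed, because 8.3 does not say so: the rate is per patient in the Dermaprazole arm.

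**Step 1: the plan's own figure.** With 65% against 20%, two-sided alpha 0.05, 80% power, 2:1 allocation, pooled variance and no continuity correction, the pooled proportion is (0.65 + 2×0.20)/3 = 0.35. Then

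n(control) = [1.96·√(1.5×0.35×0.65) + 0.8416·√(0.65×0.35 + 0.20×0.80/2)]² / 0.45² = 12.8, rounded up to 13.

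The total is 13 + 26 = 39, as stated in 8.2. The 20% is therefore a working design assumption.

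**Step 2: what the limb allows.** 2/30 = 6.7% passes. 3/30 = 10% is not below 10% and fails. At most 2 patients are allowed; 20% of 30 is 6 expected.

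**Step 3: literal reading, counting dermatitis alone.** P(pass) = Σ(k=0..2) C(30,k)·p^k·(1−p)^(30−k). At p = 0.20:
- k=0: 0.8^30 = 0.0012
- k=1: 30×0.2×0.8^29 = 0.0093
- k=2: 435×0.04×0.8^28 = 0.0337

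The sum is 0.0442, so P(fail) = 0.9558.

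**Step 4: sensitivity.**

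| Setting | P(fail the <10% limb) |
|---|---|
| true 20%, n=30 | 95.6% |
| true 20%, n=30, exactly 10% allowed | 87.7% |
| true 20%, n=26 | 91.6% |
| true 20%, n from 24 to 29 | 88.5% to 94.8% |
| true 15%, n=30 | 84.9% |
| true 10%, n=30 | 58.9% |

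An 80% chance of passing needs a true rate of about 5.2% or less.

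On the literal reading, 95.6% is a floor. Section 10.3 lists dry mouth, painful swallowing and weight loss as common with this radiation. Any patient with such an event at grade 2 or higher would also count, and the condition of no grade 3 or higher events can only lower the chance of passing.

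**Step 5: product-related reading.** None of the figures above applies, and the documents give no product-related rate. For illustration only, assumed true rates of 2%, 5% and 10% give failure probabilities of 2.2%, 18.8% and 58.9% with n=30.

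**Step 6: the same data under both readings.** Suppose 6 of 30 Dermaprazole patients have grade 2 dermatitis and none is attributed to the cream. Literal: 6/30 = 20%, so the limb fails whatever else is recorded. Product-related: these patients contribute 0/30, and the verdict rests on other events.

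**The case against.** The strongest reply is that product-related events were plainly meant. The summary, 5.6 and 8.1 use that language. The calendar in 6.1 puts the dermatitis grade and adverse events/toxicity in separate rows. Section 10.5 does not name acute, non-serious dermatitis among the events recorded regardless of relationship. Section 8.1 separates the toxicity profile from preliminary efficacy. A fully literal reading would also count ordinary chemoradiation effects and make the rule unworkable for any cream, which is evidence that it was not intended.

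Much of this stands. The literal reading is one reading, and the 95.6% is conditional on it. A reader might infer that the trial is almost certain to declare its own product unsafe; the documents do not support that, because they do not settle on the literal reading.

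What survives is that 8.3 omits the term that 8.1 uses, and nothing says which attribution levels count. With at most 2 patients allowed, whether possibly related events count can decide the verdict. The 10.3 scale does not settle this: it covers both radiation and the product, and its levels refer only to study treatment.

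A reader might also infer that 8.1 and 8.3 contradict each other, or leave rates from 10% to below 50% without a conclusion. That is not established. The reference in 8.1 to half the expected enrolment can be read as an interim look (8 or more of 15), and missing the 8.3 limits can simply mean not safe. If 8.1 were applied at the final 30, its trigger of 15 or more would already have failed 8.3 at 3. The timing is unstated, but that is a smaller matter.

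Finally, the 8.3 verdict stops nothing, and event frequencies and grades are reported anyway. That limits the harm, but the published safety conclusion would still rest on a rule with two meanings.

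**Conclusion.** The concern holds as a missing definition with a material consequence. Section 8.3 lacks an attribution term and a denominator. Applied literally, its grade 2 limb fails at least 95.6% of the time at the plan's own 20% dermatitis rate. That figure assumes 30 evaluable Dermaprazole patients, a per-patient rate, a strict limit below 10%, and dermatitis counting as toxicity. If product-related events were meant, as other wording suggests, the figure does not apply and the defect is that 8.3 does not say so. Either way, the rule should be settled before analysis, because it carries the study's stated main conclusion and the two readings can give opposite answers from the same patients.

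**What to change.** Reconcile 8.3 with 8.1, 8.2 and 10.3 before any data are analysed. Section 8.3 should state:
- that the criterion uses events attributed to the study product on the 10.3 scale, consistent with the wording of 8.1;
- which attribution levels count;
- that the rate is per patient in the Dermaprazole arm;
- how radiation dermatitis, the efficacy outcome, enters the criterion.

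Beside the verdict, report all-cause rates by arm and grade, and the between-arm comparison of the blinded dermatologist's dermatitis grades. Section 10.3 accepts that the cream might worsen dermatitis, and attribution is not described as blinded. The sponsor should also state when the 8.1 and 8.3 thresholds each apply. No cutoff or stopping rule is proposed here.

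The cost is protocol wording. Attribution (10.3) and blinded grades (6.1) are already collected. The downside is that the verdict then depends on attribution by the treating investigator or Principal Investigator, which is why the all-cause and blinded results must accompany it.

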8 STATISTICAL CONSIDERATIONS

8.1. Study Design/Endpoints

This portion of the study is designed to evaluate toxicity profile and preliminary efficacy of prophylactic Dermaprazole cream for radiation dermatitis in head and neck cancer patients receiving chemoradiation.

The first primary outcome is rates of clinically significant radiation dermatitis as defined as NCI CTCAE version 5 grade 2 or higher. Although not expected, if half our expected enrollment in the Dermaprazole group, 50% or more of patients experience moderate intervention-related toxicity, this treatment regimen will not be considered safe. The trial will be monitored for SAEs and stopped early for safety if two treatment-related grade 3 SAEs are reported or if one treatment-related grade 4-5 SAE is reported at any point of the trial for the Dermaprazole group.

Another primary endpoint will be feasibility, which is defined as the consideration of whether the protocol implementation will be successful in terms of accrual within the expected timeframe, as well as whether patients would comply with the study protocol and necessary data collection is logistically feasible in the clinical setting. To evaluate feasibility, we will measure:

Page 14 of 23

- Accrual rate and summary of causes for non-enrollment
- Percentage of patients compliant with therapy, defined as receiving at least 60Gy to the head and neck while using prophylactic Dermaprazole as directed
- Compliance rate and rate of completion of SkinDex16 forms

All endpoints will be evaluated when the last patient completes their 3 Month follow-up visit, although patients will continue with additional regular follow-up visits as described in the protocol schedule. Since by that point a patient would have completed all treatments, the data would provide accurate estimate of compliance and acute toxicity.

For the study to be considered feasible, all of the following must be true:

- No more than 5 patients fail to complete the treatment regimen due to study drug toxicity
- No more than 15 patients fail to comply to prophylactic Dermaprazole cream application of at least 80%
- Enrollment takes no longer than 24 months, and
- Proportions of analyzable questionnaires at baseline, while on-treatment, and offtreatment during follow-up, and within questionnaires completion rates are no worse than 80%, 80%, and 60% respectively.

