8.4 Reporting and Exclusions

All patients enrolled in this study who complete at least 60Gy of radiation and follow up at 30 days post treatment will be included in the analysis.

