For purposes of this study, an adverse event is considered expected when the events are those related to systems within the radiation treatment field and include: infection, allergy, or short & long-term (greater than 6 month) skin changes.

Radiation: The common side effects of radiation to the head and neck most commonly includes radiation dermatitis (i.e., erythema, blistering, pigmentation changes) and fibrosis/firmness of head and neck in the long-term. Commonly, patients develop dry mouth, changes in taste, pain when swallowing, and weight loss. Long term, some patients can continue to have changes in taste and lymphedema.

Dermaprazole: The interventional cream is not yet tested in humans and reactions *in* vivo (especially in patients experiencing radiation dermatitis) are not yet known. Possible side effects include allergy or infection. Given the success in pre-clinical studies, it is unlikely that the interventional cream would lead to worsened rates of radiation dermatitis and skin integrity, though this is a possibility.

Acute and late designations will be defined by the timing of occurrence from treatment.

- Acute toxicity will be defined as events occurring during or within 90 days of treatment completion.
- Late toxicity will be defined as events occurring or persisting ≥90 days from treatment completion.

Attribution: An attribution scale which will be utilized to attribute relatedness of the adverse event to the radiation treatment or to the Dermaprazole/Aquaphor as determined by the treating investigator or Principal Investigator. Assignment of attribution is the responsibility of the treating investigator or Principal Investigator.

Page 19 of 23

- Definite The AE is clearly related to the study treatment.
- Probable The AE is likely related to the study treatment.
- Possible The AE may be related to the study treatment.
- Unlikely The AE is doubtfully related to the study treatment.
- Unrelated The AE is clearly NOT related to the study treatment.

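### Section 8.3 would call Dermaprazole safe on observed rates alone; 30 patients cannot support that unqualified word, and the toxicity being counted is not defined

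*Combined protocol and SAP*

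**What the plan says.** The rule in section 8.3 begins "We will consider this intervention safe if there is a grade 1 toxicity rate of <50" per cent, and continues with "a grade 2 or higher toxicity rate of <10% and no grade 3 or higher events". The same section says that "the primary intention of this study is to understand the safety and tolerability profile of Dermaprazole", and section 10.3 says of the product: "The interventional cream is not yet tested in humans and reactions" in vivo are not known.

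Sections 8.1 to 8.4 attach no confidence interval, unacceptable true rate or error probability to this verdict. The only sample-size calculation (section 8.2) is for the efficacy difference, 65% against 20%.

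Two other places bear on the rule. Section 8.1 has a separate criterion: if "50% or more of patients experience moderate intervention-related toxicity, this treatment regimen will not be considered safe". That one names intervention-related events; the 8.3 rule has no attribution term. On numbers, section 8.2 enrols "until 30 patients in arm 1 and 15 patients in arm 2 have completed the course of head and neck radiation as evaluable patients", while section 8.4 says that patients "who complete at least 60Gy of radiation and follow up at 30 days post treatment will be included in the analysis".

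**The concern.** A yes-or-no safety conclusion drawn from about 30 patients depends heavily on chance, and the plan does not say how heavily. Seeing no grade 3+ event, or only two grade 2+ events, is compatible with true rates well above the plan's own limits. In a product not yet tested in humans, an unqualified finding of safety could be carried into a later trial as if those rates had been ruled out. The missing attribution term adds a second problem, because the rule behaves in opposite ways depending on which events are counted.

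**Working it through.** **The plan's own figure.** The documents give no operating characteristic for the safety rule. The one figure that can be reproduced is the efficacy sample size in section 8.2. With rates 0.65 and 0.20, two-sided alpha 0.05, power 80%, allocation 2:1 and pooled rate (0.65 + 2 × 0.20)/3 = 0.35:

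n(control) = [1.96 × √(1.5 × 0.35 × 0.65) + 0.842 × √(0.65 × 0.35 + 0.20 × 0.80/2)]² / 0.45² = 12.8, so 13 control + 26 Dermaprazole = 39. This matches the plan. It sizes the efficacy comparison and says nothing about the safety rule.

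**Inputs for the safety rule.** n = 30 Dermaprazole patients (8.2); observed grade 2+ rate below 10% and zero grade 3+ events (8.3). Since 3/30 = 10.0% fails, at most 2 affected patients pass. Assumptions: patients are independent, toxicity means intervention-related events, and the grade 1 condition is met.

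**Chance of passing the grade 2+ condition, no grade 3+ risk.** P(X ≤ 2) = Σ C(30,k) p^k (1−p)^(30−k), k = 0 to 2. At p = 0.10: 0.042 + 0.141 + 0.228 = 0.411.

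| True grade 2+ rate | Chance of passing |
|---|---|
| 5% | 81% |
| 10% | 41% |
| 12% | 28% |
| 15% | 15% |
| 20% | 4.4% |

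The probability falls as p rises, so 41% is the maximum at or above the 10% limit when n = 30.

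**When part of the 10% is grade 3+.** With probability q of grade 3+, both conditions pass with probability Σ C(30,k) (0.10−q)^k 0.90^(30−k), k = 0 to 2: 35% at q = 1 point, 30% at 2 points, 25% at 3 points, 17% at 5 points.

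**Zero grade 3+ events alone.** (1−p)^30 is 0.97^30 = 40% at a true 3% and 0.95^30 = 21% at a true 5%.

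**What passing data exclude.** Exact (Clopper-Pearson) upper limits, n = 30; for zero events the two-sided limit is 1 − 0.025^(1/30) and the one-sided limit 1 − 0.05^(1/30).

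| Observed | Two-sided 95% | One-sided 95% |
|---|---|---|
| 0/30 | 11.6% | 9.5% |
| 1/30 | 17.2% | 14.9% |
| 2/30 | 22.1% | 19.5% |

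**Sensitivity to the analysed number.** Section 8.4 can reduce n below 30. At a true 10% the chance of passing is 43% at n = 29, 46% at n = 28 and 54% at n = 25. At n = 31 three events would pass, and it is 62%.

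**The other reading.** If grade 2+ radiation dermatitis counts as toxicity, section 8.2 expects 20% in this arm. P(X ≤ 2 | 30, 0.20) = 4.4%, so the rule would nearly always fail even if the cream worked as hoped.

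**The case against.** The strongest reply is that 41% depends on a reading that 8.3 does not state. That section defines acute toxicity as adverse events during radiation or within 90 days after it, without attribution. Taken literally, radiation dermatitis counts and the practical risk is a false verdict of unsafe. This stands: the 41% is conditional, and the definition has to be settled together with the uncertainty. The intervention-related reading is nevertheless plausible, because 8.1 uses that term and 10.3 provides an attribution scale.

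Second, any rule on an observed rate passes often at its own boundary. A reader might infer from the 22.1% upper limit that a cream with twice the permitted toxicity would usually be declared safe. The calculation does not support that: at a true 20% it passes about 4% of the time. An upper confidence limit describes what the data fail to exclude; it is not a probability of a wrong verdict.

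Third, a reader might infer that the grade 1 condition protects against nothing, since it passes 98% of the time at a true 30%. But 30% lies inside the plan's 50% limit, so passing there is correct. At a true 50% that condition passes 43% of the time, and at 60% 10%.

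Fourth, section 8.2 calls this a pilot and 8.3 describes the aim as understanding the profile. Section 8.1 has serious-adverse-event stopping counts, and 10.5 provides quarterly review and independent review of any trend of three or more of the same event. So the documents do not show that patients go unmonitored, or that the sponsor treats zero events as proof. These safeguards limit the consequences, but none of them puts a bound on the true rate behind the final verdict.

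**Conclusion.** The point holds in a limited form. With 30 analysed patients and intervention-related events, the 8.3 rule can be met by data that exclude only grade 2+ rates above 22.1% and grade 3+ rates above 11.6% (two-sided 95%). That does not support an unqualified declaration of safety. The 41% is a ceiling at n = 30, reached at a true rate of exactly 10% with no grade 3+ risk; it should not be quoted as the trial's general chance of a wrong conclusion. On the literal reading that counts radiation dermatitis, the rule fails almost always, so the bound and the definition belong in one correction. The consequence is moderate: it concerns what the trial may claim, not its design or size.

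**What to change.** In section 8.3:

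1. State that the criteria apply to intervention-related events, in line with the wording of 8.1. The 50% criterion in 8.1 and the 10% criterion in 8.3 must also be reconciled; which limit is right is for the sponsor to decide.
2. Report the grade 2+ and grade 3+ rates in the Dermaprazole arm with exact Clopper-Pearson 95% intervals under one stated convention. Two-sided limits fit the plan's two-sided tests: 0/30 excludes only rates above 11.6%, and 2/30 only rates above 22.1%. The one-sided equivalents are 9.5% and 19.5%. Recompute if the analysed number is not 30.
3. Replace the declaration of safety with a statement that the preliminary tolerability criteria were met and that rates above the stated upper limit are excluded.

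This does not lower the 41% chance of meeting the criteria; it changes what meeting them may be said to show. Requiring a one-sided upper bound below 10% would cut that chance to 4.2%, but only 0/30 would then pass, and a cream with a true 5% rate would pass just 21% of the time. Under a two-sided interval even 0/30 would fail. A hard bound is therefore a poor fit for 30 patients.

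The cost is a few lines of text and one table column, with no extra patients. The downside is a less favourable headline result.
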